5.2.5.2 Treatment of allergic reactions/infusion reactions

- a. Mild allergic reactions/infusion reactions to dinutuximab infusion
 - i. A mild allergic reaction is limited to rash, flushing, urticaria, mild dyspnea – Grade 1 or 2
 - ii. The following recommendations do NOT apply to Grade 3 or 4 allergic reactions, including anaphylaxis
 - iii. Management
 - Decrease rate of dinutuximab to 50% of full rate
 - Perform serial exams at bedside
 - Administer H1 blocker (diphenhydramine, cetirizine recommended)
 - Administer H2 blocker
 - When symptoms resolve, resume original infusion rate
 - If symptoms recur when original rate is resumed, decrease to 50% rate again
 - Infusion must be stopped after 20 hours (whether the full dose of dinutuximab has been administered or not); document total amount of drug given in the 20 hour time period.
- b. Moderate to severe allergic reactions/infusion reactions to dinutuximab infusion
 - i. Moderate to severe reactions include any of the following: symptomatic bronchospasm, allergy-related edema/angioedema, hypotension, or anaphylaxis – Grade 3 or 4
 - ii. The following recommendations do NOT apply to Grade 1 or 2 allergic reactions
 - iii. Management
 - **Immediately hold dinutuximab**
 - Assess airway, breathing and circulation
 - Follow institutional guidelines for rapid response team notification if clinically indicated
 - For airway concerns

- Administer oxygen and albuterol immediately for bronchospasm
- Administer IV diphenhydramine
- Administer epinephrine (1:1000 IM recommended) immediately if upper airway involved or if airway issues are accompanied by cardiovascular collapse
- Administer IV hydrocortisone (1-2 mg/kg) if the patient has frank anaphylaxis with cardiorespiratory collapse OR if ≥ 2 doses of epinephrine are required OR if moderate to severe symptoms recur upon rechallenge with dinutuximab
- For hypotension in the setting of allergic reaction
 - Give normal saline bolus (20 mL/kg as rapidly as possible)
 - Stop or adjust doses of narcotics and sedating H1 blockers
 - Consider use of Trendelenberg position
 - See previous section for management of persistent hypotension
- For patients with mild bronchospasm or angioedema that does not impact breathing, completely resolves without the use of epinephrine and hydrocortisone and for patients whose hypotension resolves following volume bolus, dinutuximab may be resumed at 50% of the previous rate of infusion on the same day as the reaction occurred. If symptomatic angioedema or asymptomatic bronchospasm recurs when the dinutuximab is restarted, discontinue immunotherapy for that day and if symptoms/signs resolve completely that day, resume the next day with additional pre-medication of hydrocortisone 1-2 mg/kg IV. For this re-challenge, the infusion should be given in an ICU setting.
- For patients whose bronchospasm or angioedema requires the use of systemic epinephrine, protocol therapy must be discontinued.
- For patients with bronchospasm or angioedema that does not require systemic epinephrine but whose hypotension requires more extensive volume resuscitation, guidance in [Section 5.2.5.1](#) should be followed.

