5.0 DOSE MODIFICATIONS FOR TOXICITIES

In addition to dose modifications, this section provides information regarding management of toxicities known to be associated with protocol therapy.

In the sections below, when protocol therapy is to be discontinued, in general all protocol therapy should be discontinued and the patient would be taken off protocol therapy. However, if a patient requires permanent discontinuation of isotretinoin, the patient may continue on protocol therapy and receive the other therapy components (e.g., irinotecan, temozolomide, dinutuximab, GM-CSF).

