APPENDIX XI: EMERGENCY MANAGEMENT OF DINUTUXIMAB TOXICITIES

This document is for rapid reference. See [Section 5.2.5](#) for further information regarding management of acute toxicities during dinutuximab-containing cycles of therapy.

Severe Allergic Reaction

Definition (any of the following): symptomatic bronchospasm with or without urticaria, IV meds required, allergy-related edema/angioedema, or anaphylaxis (Grade 3 or 4).

Treatment:

- Immediately **hold** dinutuximab infusion
- Assess airway, breathing and circulation

For airway concerns:

- Administer oxygen and albuterol immediately for bronchospasm
- Administer diphenhydramine (if not already being given)
- Administer epinephrine immediately if upper airway involved or if airway issues are accompanied by cardiovascular collapse
- Administer hydrocortisone **if any of the following are true**
 - patient has frank anaphylaxis with cardiorespiratory collapse
 - two or more doses of epinephrine are required
 - moderate to severe symptoms recur upon rechallenge with dinutuximab

For hypotension in setting of allergic reaction:

- Hold dinutuximab and give normal saline bolus (see hypotension guidelines)
- Stop or adjust doses of narcotics
- For patients with hypotension that resolves with initial volume bolus, resume dinutuximab at half rate

Reassess need for additional volume resuscitation, ICU transfer and use of vasopressors.

For patients with angioedema that does **not** affect the airway or patients with mild bronchospasm and **no** other symptoms:

- If symptoms resolve rapidly, dinutuximab can be resumed at half rate with very close observation

Minimal criteria for resumption of dinutuximab infusion:

- Complete resolution of airway symptoms
- Complete resolution of hypotension

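### The bedside emergency card (Appendix XI) omits the rule that systemic epinephrine for bronchospasm or angioedema ends protocol therapy, and in one foreseeable case it directs resumption where Section 5.2.5.2 requires a stop

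*Combined protocol and SAP*

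**What the plan says.** **Section 5.2.5.2 (body of the protocol).** For Grade 3 or 4 reactions the instruction is "Administer epinephrine (1:1000 IM recommended) immediately if upper airway involved or if airway issues are accompanied by cardiovascular collapse". Same-day restart at half rate is allowed after mild bronchospasm, or after angioedema that does not affect breathing, if it cleared without epinephrine and hydrocortisone. The same bullet adds that "for patients whose hypotension resolves following volume bolus, dinutuximab may be resumed at 50% of the previous rate of infusion". The stop comes at once in the bullet after that: "For patients whose bronchospasm or angioedema requires the use of systemic epinephrine, protocol therapy must be discontinued". A further bullet sends children who need more extensive volume resuscitation to Section 5.2.5.1, but only where the bronchospasm or angioedema did not need systemic epinephrine. Section 5.0 explains what a stop means: "when protocol therapy is to be discontinued, in general all protocol therapy should be discontinued and the patient would be taken off protocol therapy".

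**Appendix XI (the card).** It opens with "This document is for rapid reference" and refers to Section 5.2.5 for more detail. Its airway heading says "Administer epinephrine immediately if upper airway involved or if airway issues are accompanied by cardiovascular collapse". Its hypotension heading, which concerns hypotension as part of an allergic reaction, says "For patients with hypotension that resolves with initial volume bolus, resume dinutuximab at half rate". A separate line permits half-rate restart after angioedema that spares the airway, or after mild bronchospasm with nothing else. The card ends with two minimal criteria for restarting: "Complete resolution of airway symptoms", and the same for hypotension.

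**Sections 4.4.7 and 4.5.7.** Both tell staff to obtain the card before starting dinutuximab. Both recommend having it on the unit to help with treatment decisions.

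**The concern.** The card does more than guide acute treatment. It also takes on the restart decision, with two lines that direct or permit resumption and a list of minimal criteria. The body makes epinephrine the dividing line for that decision, and the card leaves that line out.

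This matters because the card is the document most likely to be in hand during a reaction. Staff who follow its hypotension line could give the antibody again to a child whose airway reaction had just needed epinephrine, although the body takes that child off protocol therapy. The point is one of patient safety. It makes no claim about the primary endpoint or about how many children would be affected.

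**Working it through.** No arithmetic in the plan bears on this, so the check sets the two texts side by side.

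**Step 1: does epinephrine given according to the card meet the body's stop rule?** The card and Section 5.2.5.2 use the same trigger: upper-airway involvement, or airway problems with cardiovascular collapse. The body recommends the intramuscular route, which is systemic. So when the reaction is bronchospasm or angioedema, epinephrine given on this trigger by that route meets the stop rule.

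**Step 2: does the card state the stop anywhere?** Counts in Appendix XI:
- instructions to hold dinutuximab: 2
- lines that direct or permit resumption: 2
- minimal criteria for resumption: 2 (airway symptoms, hypotension)
- any form of the word *discontinue*: 0
- statements that epinephrine ends protocol therapy: 0, against 1 in Section 5.2.5.2

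**Step 3: compare directions case by case.** Cross the two features that decide the outcome.

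| Epinephrine for bronchospasm or angioedema | Hypotension that clears with one bolus | Section 5.2.5.2 | Appendix XI | Result |
|---|---|---|---|---|
| Yes | Yes | Discontinue protocol therapy | Resume at half rate | Opposite |
| Yes | No | Discontinue protocol therapy | No applicable resumption line, no stop | Card silent |
| No | Yes | Half rate allowed | Half rate directed | No conflict |
| No | No | No epinephrine stop | Nothing contrary | No conflict |

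Opposite directions: 1 of 4. Stop omitted without a contrary direction: 1 of 4. No conflict: 2 of 4.

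**Step 4: do the minimal criteria catch the first row?** They do not. Once the airway symptoms have cleared after epinephrine and the blood pressure has recovered after the bolus, the child meets both. The criteria are necessary rather than sufficient, so they create no conflict of their own, but neither mentions epinephrine.

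**Step 5: what is not in conflict.** The half-rate line taken alone agrees with the body, which also allows half rate after hypotension clears with a bolus. The card's line for airway-sparing angioedema or isolated mild bronchospasm adds no separate conflict. The problem lies in the missing exclusion.

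**The case against.** The best reply is that the card is a summary and says so. It points to Section 5.2.5, where the stop rule sits; the therapy delivery maps and Section 8.1 also send staff to Section 5.0; and nothing gives the card authority over those sections. It carries no off-protocol rules at all: it also omits the stops for prolonged pressor support and for capillary leak needing ventilation. Its silence is therefore a matter of scope. It is true that the binding rule is in the body and that the defect is an omission. But a pointer for further information does not tell a reader that a mandatory stop overrides a line on the page, and the card extends its own scope to restarting.

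A second argument is that the card's airway restart line covers only milder reactions, so the child in question falls outside it, and the card read as a whole is ambiguous. That line does permit restart only for the milder group, but it bars no one else, and the hypotension line applies on its own terms. The airway and hypotension instructions do stand under separate headings; the conflict arises because one child can fall under both.

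Third, epinephrine is also a pressor, so recovery may not be due to the bolus alone. This is a fair clinical point, but the card does not make that distinction, and staff who have just given a bolus would reasonably read the line as met.

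Fourth, the body's own hypotension clause has no epinephrine exclusion either. That is correct, but the stop follows in the very next bullet there, and the card drops it.

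Finally, one in four is a count of situations and not a rate. That is accepted.

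**Conclusion.** The concern holds. For a child with bronchospasm or angioedema treated with systemic epinephrine, and hypotension that clears with the first bolus, Appendix XI directs half-rate resumption while Section 5.2.5.2 requires discontinuation. For the same child without such hypotension, the card simply fails to state the stop.

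The finding is confined to those cases. It rests on two readings: that epinephrine given on the shared trigger by the recommended intramuscular route counts as systemic, and that the card's hypotension line applies to any child under its heading because it states no exclusion. The documents give no rate of epinephrine-treated reactions, so the number of children affected cannot be estimated. The conflict is narrow, but the case is foreseeable: the card's own epinephrine line anticipates airway problems together with cardiovascular collapse. Because the consequence is re-exposure after a serious airway reaction, it should be corrected.

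**What to change.** Add one sentence to Appendix XI: if systemic epinephrine was needed for bronchospasm or angioedema, do not resume dinutuximab; discontinue protocol therapy (Section 5.2.5.2). Make the hypotension line and the minimal criteria for resumption expressly subject to that sentence. Then redistribute the card so that copies already on inpatient units are replaced.

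The cost is one sentence and two short cross-references in an appendix, plus redistribution. No new procedures, data or patients are needed, and Section 5.2.5.2 can stand as written.

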5.2.5.3 Management of capillary leak syndrome (\geq Grade 3)

- Hold dinutuximab infusion
- Provide oxygen, fluids as needed
- Diuretics should be used with caution and hypotension avoided
- See [Section 5.2.5.1](#) for management of hypotension, anemia and hypoalbuminemia.

- Do NOT resume dinutuximab therapy if symptoms of severe capillary leak syndrome persist on the same day or subsequent days of a given cycle. Only resume dinutuximab therapy when the capillary leak syndrome resolves or requires less significant intervention (Grade 2 or less).
- If capillary leak resolves, may resume dinutuximab infusion at 50% rate the same day and for subsequent doses during a given cycle. The infusion may be given at the full rate at the start of subsequent cycles.
- If mechanical ventilation (any duration) or pressor support for ≥ 24 hours is required due to therapy-related capillary leak syndrome, the patient must discontinue protocol therapy.

5.2.5.4 Management of renal insufficiency (unrelated to hypotension)

- Consider the possibility of renal hypoperfusion in the context of borderline hypotension; administer volume if appropriate.
- If the patient's creatinine is elevated to ≥ 2 x the upper limit of normal for age/gender (see table in [Section 3.2.6.2](#)) and elevation persists despite optimized fluid management, hold dinutuximab.
- Modify dosing of concomitant medications that may contribute to or be affected by renal insufficiency.
- When urine output returns to normal and creatinine returns to < 2 x upper limit of normal for age/gender, resume dinutuximab at 50% rate. If renal function normalizes by the following day, dinutuximab may be administered at full rate. If renal function is not sufficiently improved (urine output normal and creatinine < 2 x ULN for age/gender) by Day 7, no further dinutuximab should be given during that cycle of therapy. If renal function has normalized by the planned start date for the next cycle, retreatment with dinutuximab is permitted.

5.2.5.5 Management of hyponatremia (\geq Grade 3; Na < 130 mEq/L and symptomatic or 120-124 mEq/L regardless of symptoms)

- Change hypotonic fluids to isotonic fluids as compatibilities permit
- Avoid administration of oral free water
- Correct fluid losses due to diarrhea
- 3% saline is only indicated in the following settings:
 - hyponatremia leading to seizure
 - drop in sodium level > 10 points in 6 hours or less
 - sodium level < 117 mEq/L
- If Grade 4 hyponatremia persists despite optimal fluid management, discontinue dinutuximab for the remainder of the cycle. Sodium should be monitored closely during the next cycle of therapy. If hyponatremia improves to Grade 2 or better, or baseline, empiric dose reduction is not required at the start of the next cycle of therapy, though dinutuximab would again be discontinued if Grade 4 hyponatremia were to persist despite optimal fluid management. In such cases, patient must discontinue protocol therapy.

5.2.5.6 Management of fever in the absence of hypotension

- Administer antipyretics
- Adjust fluids to account for insensible losses if fever is persistent
- Obtain blood culture
- Administer empiric antibiotics if suggested by institutional policy

5.2.5.7 Management of treatment-related pain

- No further dinutuximab therapy should be given to patients who experience treatment related Grade 3 pain that cannot be controlled by narcotics during a given cycle. Treatment with gabapentin or similar agent should be initiated if not already being administered. If pain that is not controlled with narcotics recurs during a subsequent cycle, the patient should discontinue protocol therapy.
- For patients with treatment-related Grade 3 pain requiring intravenous narcotics for ≥ 48 hours following completion of dinutuximab therapy, gabapentin or similar agent should be initiated if not already being administered. If pain requiring prolonged intravenous narcotics (≥ 48 hours following completion of dinutuximab therapy) recurs during a subsequent cycle despite this intervention, the patient must discontinue protocol therapy.

5.2.5.8 Management of visual changes

- Dinutuximab may cause impaired accommodation and/or dilated pupils with sluggish light reflex with or without photophobia. No dose modifications, dose reductions, or changes in infusion rate should be made unless there is associated vision loss. If this occurs in conjunction with Grade 3 decrease in vision, dinutuximab must be discontinued. If visual loss improves to Grade 1 or better before the next immunotherapy course is due, the patient should receive dinutuximab at a dose that is 50% reduced compared to the prior dose. Full dose sargramostim (GM-CSF) should be given. If the lower dose of dinutuximab is tolerated without worsening of ocular toxicity, full dose dinutuximab should be given in subsequent courses. If visual toxicity worsens, the patient must discontinue protocol therapy.
- Dose reductions for dilated pupils or changes in accommodation without vision loss are not required.

5.2.5.9 Management of serum sickness

- Identification of serum sickness – signs and symptoms include arthralgias/arthritis, splenomegaly, lymphadenopathy, glomerulonephritis in the presence of persistent fevers, cutaneous eruptions.
- Serum sickness typically develops 1 to 3 weeks after administration of the causative agent, but can develop within 12-36 hours in patients who have previously been sensitized to the causative agent.
- Patients with \geq Grade 3 serum sickness must discontinue protocol therapy.
- For Grade 2 serum sickness, antihistamines should be prescribed.

5.2.5.10 Management of neurotoxicity

- Patients who develop Grade 4 neurotoxicity should discontinue protocol therapy.
- Dinutuximab must be discontinued for the remainder of the current cycle of therapy for patients who develop Grade 3 sensory neuropathy or Grade 3 motor neuropathy. If abnormalities resolve by start of next cycle of therapy, the patient may receive 50% dose of dinutuximab (i.e. dinutuximab dose 8.75 mg/m²/day). If symptoms do not completely resolve or recur with dinutuximab then the patient must discontinue protocol therapy.

5.2.6 Management of Sargramostim Related Toxicities

- Hold sargramostim if total white blood cell count is > 50,000/ μ L; resume at 50% dose when the count is < 20,000/ μ L. Administer full dose with subsequent cycles and modify again if the count exceeds 50,000/ μ L.
- Localized skin reactions to sargramostim are common, and sargramostim can be continued when reactions are mild. Rotation of sites of injections is recommended rather than use of insuflon for subcutaneous injection when skin reactions occur. Consider use of antihistamines. If \geq Grade 3 injection site reactions occur, stop sargramostim for the current cycle and discontinue sargramostim for subsequent cycles of therapy.
- A syndrome characterized by respiratory distress, hypoxia, flushing, hypotension, syncope, and/or tachycardia has been reported following the administration of the first dose of sargramostim in a particular cycle. This syndrome generally resolves with symptomatic treatment and usually does not recur with subsequent doses of sargramostim in the same cycle of treatment. For safety purposes in this study, if such a “first dose reaction” occurs, the sargramostim dose will be reduced to 50% for the next dose (i.e. sargramostim dose 125 micrograms/m²/dose). If a similar reaction occurs at the 50% dose, the sargramostim will be discontinued for that patient. If the first dose at 50% does not cause any recurrent severe symptoms, subsequent doses can be escalated back to 100%. If recurrent severe symptoms are observed at 100% dose, then the dose will be reduced to 50%. If 50% is tolerated, that dose should be administered for all subsequent protocol treatment for that patient. If recurrent severe symptoms are seen at the 50% dose, the sargramostim will be discontinued for subsequent cycles of therapy.

5.2.7 Isotretinoin Specific Dose Modifications

If criteria to begin a 14-day course of isotretinoin are not met by the date the therapy is due to begin, delay therapy for one week. If criteria are still not met, hold therapy until criteria are met. If an observed toxicity is possibly, probably or definitely due to isotretinoin, reduce the isotretinoin dose to 125 mg/m²/day divided BID for patients with BSA \geq 0.6 m² (for patients < 0.6 m² BSA see suggested Dose Reduction 1 in the table below). An additional dose reduction to 100 mg/m²/day divided BID for patients with BSA \geq 0.6 m² (for patients < 0.6 m² BSA see suggested Dose Reduction 2 in the table below) should occur if criteria are still not met one week after the due date for subsequent cycles and the toxicity is possibly, probably or definitely due to isotretinoin.

Note: If there is a delay in beginning isotretinoin, patients need to maintain at least one week off isotretinoin before starting the next cycle of protocol therapy). Missed doses of isotretinoin should **NOT** be made up during the one week break between the scheduled end of isotretinoin therapy and the start of chemotherapy in the subsequent cycle to avoid delays in therapy.

SUGGESTED ISOTRETINOIN DOSE REDUCTION		
BSA (m ²)	Dose Reduction 1	Dose Reduction 2
0.25-0.29	10 mg PO BID x 4 days/wk and 10 mg PO once daily x 3 days/wk	10 mg PO daily x 6 days/wk and 10 mg PO BID x 1 day/wk
0.3-0.39	20 mg PO BID x 4 days/wk and 10 mg PO BID x 3 days/wk	10 mg PO BID x 6 days/wk and 20 mg PO BID x 1 day/wk
0.4-0.49	20 mg PO BID x 5 days/wk and 30 mg PO BID x 2 days/wk	20 mg PO BID x 5 days/wk, 10 mg PO BID x 2 days/wk
0.5-0.59	30 mg PO BID	20 mg PO BID

Decrease isotretinoin dose to 125 mg/m²/day (see suggested Dose Reduction 1 in the table above for patients with BSA < 0.6 m² or reduce dose by ~25%) for subsequent cycles for the occurrence of any Grade 3 or 4 toxicities possibly, probably, or definitely attributable to isotretinoin EXCLUDING:

- Grade 3 or 4 hematologic toxicities
- Grade 3 hepatic toxicity
- Grade 3 nausea and vomiting
- Grade 3 fever

If the same Grade 3 or 4 toxicity recurs at 125 mg/m²/day, decrease dose to 100 mg/m²/day (see suggested Dose Reduction 2 in the table above for patients with BSA < 0.6 m² or reduce dose by ~25%). If the same toxicity recurs at 100 mg/m²/day (Dose Reduction 2), discontinue isotretinoin. Patients can continue to receive protocol therapy with irinotecan, temozolomide, dinutuximab, and GM-CSF, and isotretinoin will be omitted from the remaining cycles of protocol therapy.

If serum creatinine at the time of the planned start of isotretinoin during Cycles 2-6 is > 2x baseline value documented at the start of Post-Consolidation therapy, a creatinine clearance (or nuclear medicine GFR) should be done prior to starting isotretinoin. If the creatinine clearance and/or GFR are < 50 mL/min/1.73 m², decrease the isotretinoin dose by 50%, and monitor serum creatinine twice per week. If the patient develops worsening hematuria, and/or proteinuria, hypertension, and/or a further increase in creatinine, hold isotretinoin until these parameters return to baseline levels.

If the patient develops > Grade 1 hematuria, > Grade 1 proteinuria, and/or > Grade 1 hypertension during any cycle of therapy, hold isotretinoin until these symptoms resolve or return to baseline. Please refer to [Section 5.2.8](#) for isotretinoin administration in the setting of TA-TMA.

For localized cheilitis, topical agents (e.g., Vitamin E) may be applied to lips for subsequent cycles. If this does not control symptoms sufficiently to allow oral intake, decrease the isotretinoin dose to 125 mg/m²/day for patients with BSA

$\geq 0.6 \text{ m}^2$ (for patients $< 0.6 \text{ m}^2$ BSA see suggested Dose Reduction 1 in the table above or reduce dose by ~25%).

If fasting serum triglycerides are $> 500 \text{ mg/dL}$ when isotretinoin is due to begin, hold isotretinoin and repeat fasting triglyceride level. If triglycerides remain $> 500 \text{ mg/dL}$, start medical therapy for serum triglyceride reduction and begin isotretinoin (full dose) when triglycerides are $\leq 500 \text{ mg/dL}$. If triglycerides are still $> 500 \text{ mg/dL}$ by the time the next cycle of isotretinoin is due, then reduce dose to $125 \text{ mg/m}^2/\text{day}$ for patients with BSA $\geq 0.6 \text{ m}^2$ (for patients $< 0.6 \text{ m}^2$ BSA see suggested Dose Reduction 1 in the table above or reduce dose by ~25%) for subsequent cycles.

Isotretinoin has been associated with pseudotumor cerebri. This drug should be discontinued in patients who are found to have papilledema.

